10.5 Reporting Adverse Events

Identification and collection of anticipated and unanticipated adverse event information is the responsibility of the study investigator. All unanticipated adverse events should be documented by completing the Adverse Event Case Report Form. and submitted to the study coordinating site per study Manual of Procedures. All adverse events (**whether anticipated or unanticipated**) should be reported to the Institutional Review Board according to site guidelines.

The identification and collection of serious adverse events is the responsibility of the study investigator. All serious adverse events should be documented by completion of the Serious Adverse Event Case Report Form. All Serious Adverse events should be reported to the Medical Monitor within 24 hours of the site's notification of the event and to the Institutional Review Board according to site guidelines.

10.6 Follow-up of Adverse Events

The investigator is responsible for recommending the type and duration of follow-up for each subject who experiences an adverse event. All unanticipated events must be followed until study completion or adverse event resolution or stabilization of adverse event sequelae if the unanticipated adverse event(s) persists post study completion. All follow-up must be documented and submitted to the study coordinating site via the Adverse Event Case Report Form within the appropriate time frames per the study Manual of Operations.

10.7 Aggregate Review of Adverse Events

The Medical Monitor will be responsible for the continuous review of unanticipated adverse events.

11. Statistical Considerations

This prospective, two-arm, unmasked, randomized, controlled trial will evaluate and compare the clinical outcomes after implantation of the porous plate (polyethylene) Ahmed Glaucoma Valve (M4) with the silicone plate Ahmed Glaucoma Valve (FP7) in patients with intractable glaucoma. Subjects will be randomized in a 1:1 ratio to one of two surgical intervention arms - surgical intervention with the Model FP7, Silicone Plate Ahmed Glaucoma Valve (Group A) or the Model M4, Porous Plate Ahmed Glaucoma Valve (Group B). The computer-generated randomization scheme (using varying block sizes of 2 to 4) will be completed by a staff member of the University of Virginia, Department of Ophthalmology, whose sole role in this study is to generate the randomization scheme. The subject surgical intervention arm assignment will be placed in a sealed envelope, securely delivered to the sites, and will be accessed by the site study staff in the site Surgical Admission Suite immediately prior to local anesthesia injection for the surgical procedure. Post-randomization, the assigned surgical intervention arm will be unmasked to the subject.

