5.2 Secondary Endpoints

- (a) The mean number of anti-glaucoma medications in the porous plate group as compared to the silicone plate group at 12 months.
- (b) Surgical success in the porous plate group as compared to the silicone plate group at 12 months. Surgical success is defined as:

Unqualified surgical success: 5 mmHg < intraocular pressure < 22 mmHg with no loss of light perception and no additional glaucoma procedures or glaucoma medications.

Qualified surgical success: 5 mmHg < intraocular pressure < 22 mmHg with no loss of light perception and no additional glaucoma procedures, but with the adjunctive use of glaucoma medications.

6. Study Synopsis

Title:	Comparison of Silicone and Porous Plate Ahmed Glaucoma Valves
Study Period:	12 months, 9 visits: Screening/Baseline; Day of Surgery; Post-Operative Days 1 and 7; and Post-Operative Months 1, 3, 6, 9, and 12. Unscheduled visits will be performed and recorded as required for the optimal treatment and follow up of the subject.
Study design:	A prospective, two-arm, unmasked, randomized, controlled study.
Objectives:	A prospective, randomized trial to evaluate and compare the clinical outcomes after implantation of the porous plate (polyethylene) with the silicone plate Ahmed Glaucoma Valve in subjects with intractable glaucoma.
Control Arm:	Subjects undergoing surgery with the silicone plate Ahmed Glaucoma Valve (Model FP7)
Treatment Arm:	Subjects undergoing surgery with the porous plate Ahmed Glaucoma Valve (Model M4)
Subject Population:	Patients with intractable glaucoma who are candidates for valve surgery.
Sample Size:	Total of 88 subjects with a planned 40 subjects in each arm. Each site can enroll a maximum of 40 subjects.
Follow-up duration:	12 months.

7. Study Population

This is a prospective, two-arm, unmasked, randomized, controlled study of 80 enrolled subjects with intractable glaucoma that have not responded to conventional medical and surgical therapy. The study will accrue up to 88 subjects to allow for a dropout rate of 10 %.

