8.1 Screening Visit / Baseline Evaluation (Days -60 to -1)

After obtaining informed consent in the patient's, all potential subjects will undergo a baseline examination to determine study eligibility. Standard-of-care evaluations for glaucoma patients that are documented by the investigator may be utilized as the baseline evaluation to determine subject eligibility, provided the evaluations occur within 60 days prior to the planned surgical intervention, even if these evaluations occur prior to the subject consenting to participate in the study. This avoids the potentially unnecessary repetition of screening evaluations that are a part of the standard-of-care for glaucoma patients.

The following examinations, tests, and procedures are required as part of the baseline evaluation to determine subject eligibility and must be conducted within 60 days of the planned surgical intervention:

- Signing of the informed consent
- Review of Inclusion / Exclusion Criteria
- Demographic Information (Date of Birth, Sex, Self-Identified Ethnicity)
- Type of Glaucoma (Diagnosis)
- Review of Medical and Ocular Surgical History
- Review of Concomitant Systemic Medications
- Review of Concomitant Glaucoma Medications
- Review of History of Previous Glaucoma Treatments (laser and surgery)
- Review of Other Concomitant Ocular Medications
- Manifest Refraction and Snellen Visual Acuity
- Intraocular Pressure
 - Intraocular Pressure will be measured utilizing Goldmann applanation tonometry. Two consecutive measurements will be obtained and the mean of those two measurements will be considered the subject's baseline intraocular pressure. The intraocular pressure should be performed at the same time of day at all visits, when possible.
- Slit Lamp Examination
- Gonioscopy

- Funduscopy Examination
- 30-2 or 24-2 SITA Standard Humphrey Visual Field (if available, and may be used if obtained within 12 months of the planned surgical intervention)
- Determination of the study eye and subject eligibility (if both eyes qualify, the study eye will be the eye with the highest baseline intraocular pressure, then worst baseline visual acuity, then the right eye; unless in the investigator's best judgment the other eye should be selected)
- Urine or Serum Pregnancy Test for women of child-bearing potential (to be conducted as part of the site's standard pre-operative testing). The test must be negative to be eligible to participate.

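### Block sizes of 2 to 4 are printed in the protocol of an unmasked trial; if lists are separate per site and no earlier patient is pending, about 55% of assignments can be predicted with at least 75% certainty

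*Combined protocol and SAP*

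**What the plan says.** Section 11 (Statistical Considerations) calls the study "This prospective, two-arm, unmasked, randomized, controlled trial" and states: "Subjects will be randomized in a 1:1 ratio to one of two surgical intervention arms". The list is computer-generated "using varying block sizes of 2 to 4" by a staff member with no other study role. Each assignment is "placed in a sealed envelope, securely delivered to the sites". Opening comes late in the process: the envelope "will be accessed by the site study staff in the site Surgical Admission Suite immediately prior to local anesthesia injection". The section ends: "Post-randomization, the assigned surgical intervention arm will be unmasked to the subject".

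Section 6 adds: "Each site can enroll a maximum of 40 subjects". Section 8.2 puts randomization on the day of surgery, which must fall within 60 days of completed screening. Section 8.1 gives a default rule for the study eye, which applies "unless in the investigator's best judgment the other eye should be selected".

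The documents do not say whether each site has its own list or how often each block size is used. They give no figure for how predictable the assignments are.

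**The concern.** Opening the envelope at the last moment hides its contents. It does not hide what can be inferred from earlier envelopes. In an unmasked trial the site knows which device each earlier patient received. With very small blocks of published size, a lead for one device on the site's list strongly suggests that the other device comes next.

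Someone with a preference could use this when deciding which waiting patient goes to surgery next, and so place patients with a better outlook in one arm. The primary comparison of mean intraocular pressure at 12 months is powered for a difference of 1.5 mmHg (Section 11.1), so a modest imbalance in prognosis would matter. Nothing in the conduct of the trial requires the sites to know the block sizes.

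**Working it through.** The plan has no predictability figure to reproduce, so the check starts from its inputs.

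**Inputs.** From the documents: 1:1 allocation, block sizes 2 to 4, no masking, site-held envelopes (Section 11), and at most 40 subjects per site (Section 6). Assumed: sizes 2 and 4 only, since these are the sizes that balance at 1:1; equal mix, with 2:1 and 1:2 as the range; a separate list per site; every earlier assignment known when the next patient is chosen.

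**Closed form.** Every block is balanced, so the running difference between arms over the whole list equals the difference within the current block. The observer need not know where blocks begin and guesses the arm that is behind.

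- Positions preceded by an imbalance: a block of 2 has 1. A block of 4 has six equally likely orders; two of them (AABB, BBAA) give 3 such positions and four give 2, a mean of (2×3 + 4×2)/6 = 7/3. Share: (1 + 7/3)/(2 + 4) = 55.6%.
- Certainty of such a guess after the first assignment of a block known to be starting: ½×1 + ½×⅔ = 83%. With a 1:2 mix: ⅓×1 + ⅔×⅔ = 78%. In the simulation below these were the lowest values, so every such guess passes 75%.
- Correct guesses overall: a block of 2 gives 0.5 + 1 = 1.5. A block of 4 gives 0.5 + ⅔ + ⅔ + 1 = 2.83. Rate: (1.5 + 2.83)/6 = 72.2%.

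**Simulation.** A Bayesian observer knows the sizes and all past assignments but not the block boundaries (3,000 lists of 40). Result: 55% predictable at 75% or more, about 10% certain, 72% guessed correctly. The 55% becomes 54-56% across mixes of 2:1 to 1:2 and 54-55% for lists of 10 to 80. If all blocks were of size 4, it would be 33%.

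**Relaxing the assumptions (sizes 2 and 4, equal mix).**

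| Situation | Predictable at ≥75% | Correct overall |
|---|---|---|
| Separate list per site, nobody pending | 55% | 72% |
| Shared list, site sees half of patients | 19% | 60% |
| Shared list, site sees a third | 13% | 57% |
| Shared list, site sees a fifth | 9% | 55% |
| Separate list, one earlier patient pending | 5% | 55% |
| Separate list, two earlier patients pending | 0% | 53% |

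**After the change (separate lists, nobody pending).** The undisclosed column assumes an observer with a flat prior on even sizes 2 to 10.

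| Sizes used | ≥75%, sizes disclosed | ≥75%, undisclosed | Certain, undisclosed | Correct overall |
|---|---|---|---|---|
| 2, 4 (now) | 55% | n/a | n/a | 72.1% |
| 4, 6 | 48% | 24% | 0% | 68.9% |
| 4, 6, 8 | 35% | 29% | 0% | 67.6% |
| 6, 8 | 30% | 33% | 0% | 66.8% |

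The share predictable at 75% or more falls by (55−33)/55 = 40% to (55−24)/55 = 56%. The excess of correct guesses over chance falls from 22.1 points to 18.9, 17.6 and 16.8, a cut of 14% to 24%. Backing the arm that is behind still works without knowing the sizes.

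**Larger blocks with one earlier patient pending.** Sizes 4, 6 and 8 give 14% (undisclosed) to 16% (disclosed) predictable at 75% or more, against 5% for sizes 2 and 4.

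**The case against.** The strongest reply is that the 55% needs conditions the plan does not state and may often not meet. Separate site lists are suggested by site-held envelopes but written nowhere. Eligibility and study eye are settled at screening, up to 60 days before surgery, while randomization waits for the operating day. Section 11.4 expects 15 patients a month and foresees several in screening at once, so earlier patients will often be pending. This stands. It means the 55% should not be applied to decisions about whom to enrol or which eye to choose without that condition.

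The plan also has real safeguards: an independent list generator, sealed envelopes, late opening, and an email to the coordinating site before each randomization (Section 12, for accrual monitoring). None of them stops inference from past assignments when choosing whose surgery comes next among patients already screened. The baseline comparison in Section 11.2, with change from baseline if needed, partly addresses steering on measured pressure but not on unmeasured prognosis.

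A reader might infer more than the documents support:

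- *That larger undisclosed blocks would halve selection bias.* They roughly halve confident prediction only.
- *That the trial carries a bias of 0.88 mmHg.* That figure arises if someone steers prognosis by ±1 mmHg on every best guess: 2×(2×0.72 − 1) = 0.88, against 2×(2×0.676 − 1) = 0.70 with sizes 4, 6 and 8. The ±1 mmHg has no source in the documents, so this is an illustration and not an estimate.
- *That steering has occurred.* Nothing in the documents shows it.
- *That a block of 3 contradicts 1:1.* The phrase is naturally read as sizes 2 and 4.

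**Conclusion.** The point holds as a conditional vulnerability. The protocol discloses very small block sizes to unmasked site staff who know past assignments. With separate site lists, sizes 2 and 4 in roughly equal mix, and no earlier patient pending, about 55% of assignments are predictable with at least 75% certainty, about 10% are certain, and 72% are guessed correctly. The exposure lies mainly in the order of surgery. It shrinks to 9-19% under a shared list and to about 5% with one patient pending. The documents do not settle which situation applies. The concern merits action because the protection costs almost nothing, not because a bias of known size has been shown.

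**What to change.** Three changes to Section 11:

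1. Delete the block sizes, say only that block sizes vary at random, and keep the sizes in the list generator's restricted file.
2. State whether each site has its own list.
3. Generate envelopes not yet issued with larger, randomly varying even blocks, for example 4, 6 and 8.

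The cost is a new computer-generated list, one deleted phrase and one added sentence. There are two downsides. The imbalance at the end of a list can reach 4 subjects per site (half of a block of 8), against 2 with blocks of 4; the effect on power is negligible. And larger blocks are somewhat easier to guess than blocks of 2 and 4 when an earlier patient is pending, so the sponsor should weigh how often that will be so at its sites.

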11.1 Sample Size Considerations

With a sample size of 40 in each group, the power of the study will be 0.8 (80%) to detect a 1.5 mmHg difference in intraocular pressure with a standard deviation of 3 mmHg. Investigators will screen and treat patients until the study is fully enrolled or the study is terminated. All subjects undergoing surgical intervention will be entered in the statistical analysis. Based on prior studies, failure to complete the 12 month post-operative period is not likely to exceed 10% of randomized subjects.

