11.4 Accrual

Maximum study accrual is estimated to be 88 subjects to accrue the targeted 80 subjects required to meet the study objectives. Maximum accrual allows for a 5% ineligibility rate and a 5% rate of coming off study before the planned surgical intervention. Once target accrual is reached, the study allows those within the screening process to be enrolled. As this allowance is not to exceed 4 patients, up to 84 patients may be treated with Ahmed Glaucoma Valves. Based upon accrual rates to prior drainage

implant studies, accrual is estimated at 15 per month; thus, accrual to the study should be completed in less than 6 months.

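### The stated 80% power is wrong: 40 per arm with SD 3 mmHg gives about 60% power for 1.5 mmHg, and about 55% if 10% of 80 treated subjects are lost by month 12

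*Combined protocol and SAP*

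**What the plan says.** Section 11.1 gives the whole sample-size justification in one sentence: "With a sample size of 40 in each group, the power of the study will be 0.8 (80%) to detect a 1.5 mmHg difference", "with a standard deviation of 3 mmHg". It gives no significance level and does not say whether the 3 mmHg is the SD of month-12 pressure, of change from baseline, or of something else.

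The comparison being powered is clear from other sections. Section 5.1 makes the primary endpoint mean intraocular pressure at 12 months, one arm against the other. Section 11 randomizes 1:1 to two separate arms. Section 11.2 names a two-tailed test and calls it paired.

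Three places deal with loss of subjects:

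- Section 7: "The study will accrue up to 88 subjects to allow for a dropout rate of 10" percent.
- Section 11.4: "Maximum accrual allows for a 5% ineligibility rate and a 5% rate of coming off study before the planned surgical intervention". The same section sets 80 as the number the study needs and allows at most 84 to be treated.
- Section 11.1: "failure to complete the 12 month post-operative period is not likely to exceed 10% of randomized subjects".

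**The concern.** A difference of 1.5 mmHg with SD 3 mmHg is a standardized effect of 0.5. Two independent groups need 63 or 64 subjects each to detect that with 80% power at the usual two-sided 5% level, so 40 per group is well short.

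The 1.5 mmHg difference is the only design target in the plan. If the trial finds no significant difference, a reader who trusts the 80% will take that as fair evidence against a difference of this size. The true risk of missing it is about twice what the plan states.

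The accrual figures add to the problem. Randomization takes place on the day of surgery (Section 8.2), so losses before surgery and losses of randomized subjects during follow-up are different losses. One margin of eight subjects is described as covering each.

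**Working it through.** **Inputs.** n = 40 per arm, difference 1.5 mmHg, SD 3 mmHg, stated power 0.80 (Section 11.1); 1:1 allocation (Section 11); two-tailed test (Section 11.2). Alpha = 0.05 is an assumption, because the plan gives none.

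**Step 1: attempt to reproduce 80%.** For two independent means the noncentrality parameter is

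δ = difference / (SD × √(2/n)) = 1.5 / (3 × √(2/40)) = 2.236.

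- Normal approximation: power ≈ Φ(2.236 − 1.960) = Φ(0.276) = 0.609.
- Exact noncentral t, 78 degrees of freedom, critical value 1.991: power = 0.598.

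The stated 0.80 is not reproduced.

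**Step 2: other readings of the same inputs (noncentral t).**

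| Reading | Power |
|---|---|
| Independent arms, 40 each, two-sided 0.05 | 59.8% |
| Independent arms, 40 each, one-sided 0.05 | 71.6% |
| Independent arms, 40 each, two-sided 0.20 | 82.7% |
| All 88 analysed, 44 each, two-sided 0.05 | 64.0% |
| 40 pairs, SD of the differences 3 mmHg | 86.9% |
| 40 pairs, SD 3 mmHg per measurement, correlation 0 / 0.3 / 0.5 | 58.7% / 74.1% / 86.9% |

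Reading the 3 mmHg as the SD of change from baseline leaves the two-arm result at 59.8%. The paired rows do not describe this design, since no subject in one arm is matched to a subject in the other.

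**Step 3: what 80% would need.**

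- Sample size by the normal formula: n = 2 × (1.960 + 0.842)² × 3² / 1.5² = 62.8, so 63 per arm. By exact t, 64 per arm (power 0.801).
- With 40 per arm and SD 3 mmHg, the difference detectable with 80% power is 1.90 mmHg.
- With 40 per arm and 1.5 mmHg, the SD would have to be about 2.36 mmHg, or two-sided alpha about 0.167.

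**Step 4: loss by month 12.**

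| Account of the numbers | Evaluable at month 12 | Power for 1.5 mmHg |
|---|---|---|
| Section 11.4, 80 treated, 10% lost | 80 × 0.90 = 72 (36 per arm) | 55.3% |
| Section 11.4, cap of 84 treated, 10% lost | 84 × 0.90 = 75.6 (about 38 per arm) | 57.6% |
| Section 7, 88 randomized, 10% lost | 88 × 0.90 = 79.2 (about 39.6 per arm) | about 59% |

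Section 11.4's own rates give 88 × 0.95 × 0.95 = 79.4 operated, so that section uses up the whole margin before surgery. A further 10% loss leaves 79.4 × 0.90 = 71.5. At 36 per arm the difference detectable with 80% power is 2.01 mmHg.

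**Step 5: type II error.** 1 − 0.598 = 0.402 with no loss and 1 − 0.553 = 0.447 at 36 per arm, against a stated 0.20.

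**The case against.** The strongest defence is that the plan leaves several inputs open.

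- **Alpha.** It is never stated, so 5% two-sided is an assumption. But one-sided 5% still falls short at 71.6%, and reaching 80% takes a two-sided level near 0.167, which is not a conventional choice.
- **The paired test.** Section 11.2 names a paired t-test. With an SD of differences of 3 mmHg, 34 pairs already give 80.8%, so a claim of at least 80% would be true on that reading. With SD 3 mmHg per measurement and a correlation near 0.39, 40 pairs give about 80%. This may be where the figure came from, but it does not support it, because the arms are independent.
- **The size of the loss.** Ten percent is an upper bound, Section 7's account keeps power near 59%, and Section 8.5 asks withdrawing subjects for a visit with the month-12 tests. So 55% is the low end of a 55 to 60% range. The plan gives no rule for using early-withdrawal values or for handling missing month-12 pressures, so the loss cannot be dismissed.
- **The consequence.** The hypothesis is one of superiority and no equivalence claim is planned. A reported confidence interval would show what the data exclude. That limits the harm but does not make the power statement correct.
- **Baseline adjustment.** It could raise power, but a baseline correlation of 0.3 gives only about 64%, and about 0.62 is needed for 80%. The plan has only a conditional change-from-baseline analysis.

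**Conclusion.** The concern holds. With the plan's own sample size, difference and SD, power for two independent arms is 59.8%, not 80%. This assumes two-sided alpha 0.05. No reading with independent arms and a conventional alpha, one-sided 5% included, reaches 80%.

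Allowing for the loss that Section 11.1 expects, power is between 55% and 60%, depending on how much loss occurs and which account of the 88 is followed. The 55.3% applies to 80 treated with the full 10% lost and no usable month-12 value from those subjects.

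Sections 7 and 11.4 contradict each other on the purpose of the extra eight subjects. On the Section 11.4 account, even the cap of 84 treated leaves about 76 at month 12, short of the 80 which that section sets as its target.

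This must be fixed: it is the power statement for the primary endpoint, and it understates the type II error by about half.

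**What to change.** Replace the power sentence in Section 11.1 with text along these lines: *With 40 evaluable subjects per arm, an SD of 3 mmHg and a two-sided significance level of 0.05, the study has about 60% power to detect a difference of 1.5 mmHg and 80% power to detect 1.9 mmHg. With 10% loss by month 12 (36 per arm), these become about 55% and 2.0 mmHg.* The significance level must be confirmed by the sponsor, since it is not in the plan now. The text should also say what the 3 mmHg is the SD of.

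Reconcile Sections 7, 11.1 and 11.4: assign the margin from 80 to 88 either to losses before surgery or to dropout by month 12, and state the evaluable number expected at month 12.

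The cost is wording in the protocol and SAP, and a less favourable stated power or detectable difference. No extra enrolment is needed for the statement to be correct. If the sponsor prefers to keep 80% power for 1.5 mmHg, that takes 64 evaluable per arm, or 64 / 0.90 = 71.1, so 72 per arm randomized. A prespecified baseline-adjusted analysis would recover part of the power, by an amount that depends on a baseline correlation the documents do not give.

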8.6 Schedule of Visit Tests and Procedures

	SCR ²	Day 0	POD 1	POD 7	Mo 1	Mo 3	Mo 6	Mo 9	Mo 12/ Early Term	Un- sched Visit
Informed Consent	X									
Inclusion/ Exclusion Criteria Review	X									
Demographic Information	X									
Glaucoma Diagnosis	X									
Review of Medical & Ocular Surgical History	X									
Review of Concomitant Systemic Medications	X									
Review of Concomitant Glaucoma Medications	X									
Review of History of Previous Glaucoma Surgeries	X									
Review of Other Concomitant Ocular Medications	X									
Manifest Refraction & Snellen Visual Acuity	X		X	X	X	X	X	X	X	X ³
Intraocular Pressure	X		X	X	X	X	X	X	X	X ³
Slit Lamp Examination	X		X	X	X	X	X	X	X	X ³
Gonioscopy	X					X	X	X	X	X ³
Funduscopy Examination	X		X	X	X	X	X	X	X	X ³
Visual Field Test	X									
Study Eye Determination	X									
Pre-operative tests (labwork, EKG, physical exam) ¹	X									
Randomization		X								
Surgical Intervention		X								
Concomitant Medication Review			X	X	X	X	X	X	X	X ³
Adverse Event Review			X	X	X	X	X	X	X	X ³
Ultrasound Biomicroscopy or Anterior Segment OCT ³							X	X	X	X ³

1. A serum or urine pregnancy test is required for women of child-bearing potential only, prior to randomization.
2. All Screening Exams must be completed within 60 days of the planned Surgical Intervention, except the visual field test which must be completed within 12 months of the planned Surgical Intervention.
3. Optional.

9. Concomitant Medications and Procedures

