11.2 Assessment of the Primary Endpoint

The primary efficacy endpoint is the mean intraocular pressure in the porous plate group as compared to the silicone plate group at 12 months. The analysis will compare the changes of intraocular pressure after the surgical intervention in the porous plate group as compared to the silicone plate group. Baselines will be compared to check for statistically significant differences and, if needed, a change from baseline analysis will be performed. The statistical significance of the differences in intraocular pressure will be determined using two-tailed paired t-tests.

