11.6 Plans for Final Analysis

Subjects will be monitored until they complete the study period. Primary analysis will include all subjects undergoing the study surgical intervention. All subjects who receive any study intervention will be monitored for adverse events. Adverse event information will be tabulated by type and severity of adverse events. If the subject is determined to be a treatment failure (e.g., increased intraocular pressure, hypotony, loss of light perception vision, or additional glaucoma surgery), this will be documented in the study database.

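### The plan promises an analysis of all operated subjects but does not say how a subject without a Month-12 IOP enters the primary t-test, or whether an early-withdrawal reading counts as Month 12

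*Combined protocol and SAP*

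**What the plan says.** All references are to the combined protocol and SAP.

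- **Analysis set.** Section 11.1: "All subjects undergoing surgical intervention will be entered in the statistical analysis". Section 11.6: "Primary analysis will include all subjects undergoing the study surgical intervention".
- **Endpoint and test.** Section 11.2: "The primary efficacy endpoint is the mean intraocular pressure in the porous plate group as compared to the silicone plate group at 12 months". The test follows: "The statistical significance of the differences in intraocular pressure will be determined using two-tailed paired t-tests". If baselines differ, a change-from-baseline analysis is allowed; it also needs the 12-month reading.
- **Expected loss.** Section 11.1 puts failure to complete 12 months at no more than about 10% of randomized subjects, not split by arm.
- **Early withdrawal.** Section 8.5 says a subject who withdraws should have a visit with the Month-12 assessments. The Section 8.6 schedule gives that visit and Month 12 one column, "Mo 12/ Early Term". Neither section says how the reading is analysed.
- **Other IOP data.** Section 8.3 schedules IOP on Days 1 and 7 and at Months 1, 3, 6, 9 and 12. Section 11.2 gives the intermediate readings no role.
- **Not found anywhere.** There is no imputation rule, carry-forward rule, repeated-measures model or missing-data sensitivity analysis for the primary endpoint.

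**The concern.** The analysis set and the named method do not fit together. A t-test at one time point has no means of including a subject who has no value there. Someone must then choose between leaving such subjects out, which breaks Sections 11.1 and 11.6, and entering an early-withdrawal reading as if it were Month 12. The second is not the stated endpoint: the background section describes a transient early post-operative pressure rise, so an early-exit reading can differ systematically from a 12-month one.

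The plan leaves that choice open in a trial where the arm is known. If eyes with poor pressure control leave more often in one arm, the comparison shifts, in a direction that depends on which arm loses them.

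**Working it through.** **Inputs from the plan.** 40 per arm, difference 1.5 mmHg, SD 3 mmHg, loss up to 10% (all Section 11.1).

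**Assumed, not in the documents.** The split of loss between arms, the correlation between visits (ρ = 0.5 to 0.7), and the dropout mechanism.

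**Step 1: the plan's own figures.** Expected loss is 0.10 × 80 = 8 subjects, leaving 72. The stated power ("the power of the study will be 0.8 (80%) to detect a 1.5 mmHg difference in intraocular pressure with a standard deviation of 3 mmHg") does not reproduce. The standard error is 3 × √(2/40) = 0.671 and 1.5/0.671 = 2.236. Then 2.236 − 1.960 = 0.276, which gives about 61% at an assumed two-sided 5% level. That is a separate matter; only the 1.5 and the 3 are used below.

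**Step 2: complete-case bias in closed form.** Suppose a share p of an arm is missing, drawn at random from eyes above that arm's median Month-9 IOP. The mean of a standard normal above its median is √(2/π) = 0.798. The missing eyes' Month-12 mean then exceeds the arm mean by s = ρ × 0.798 × 3, and the observed mean falls by s × p/(1 − p).

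- ρ = 0.5: s = 1.197. ρ = 0.7: s = 1.676.
- 10% vs 10%: both arms fall equally, so the bias is 0.
- 15% (higher-IOP arm) vs 5%: 0.15/0.85 − 0.05/0.95 = 0.1239. Bias is 0.1239 × 1.197 = 0.15 or 0.1239 × 1.676 = 0.21. Estimate 1.35 or 1.29.
- 20% vs 0%: 0.20/0.80 = 0.25. Bias is 0.30 or 0.42. Estimate 1.20 or 1.08.

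**Step 3: simulation of the same setting** (at least 2,000 trials per scenario; repeat runs agree to within about 0.03). The earlier-visit estimate is a regression on Months 3 to 9, standing in for the mixed model.

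| Loss, higher-IOP arm vs other | Complete-case, ρ = 0.5 / 0.7 | Using earlier visits |
|---|---|---|
| 10% vs 10% | about 1.5 / 1.5 | about 1.5 |
| 15% vs 5% | 1.36 / 1.30 | about 1.5 |
| 20% vs 0% | 1.22 / 1.10 | about 1.5 |
| 0% vs 20% | 1.79 / 1.91 | about 1.5 |

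The standard error of the complete-case estimate is about 0.70. The 15% vs 5% bias is 1.5 − 1.36 = 0.14 to 1.5 − 1.30 = 0.20 mmHg, and 0.20/0.70 = 0.29 standard errors.

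**Step 4: loss that depends on the unseen Month-12 IOP.** Set ρ = 1 in step 2, so s = 2.394. Complete-case gives 1.5 − 0.1239 × 2.394 = 1.20 at 15% vs 5%, and 1.5 − 0.25 × 2.394 = 0.90 at 20% vs 0%. The earlier-visit estimate gives 1.30 to 1.41 and 1.11 to 1.27: closer to 1.5, but not unbiased.

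**Step 5: equal rates are not a guarantee.** In general the bias has size pA·DA − pB·DB, where D is the missing-minus-observed mean in an arm. With 4 of 40 missing in each arm and assumed gaps of 10 and 0 mmHg, it is 0.10 × 10 − 0.10 × 0 = 1.0 mmHg.

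The bias from entering early readings as Month 12 is not quantified; it would need a time course of IOP that the documents do not give.

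**The case against.** A reader might infer that the t-test discards everyone who leaves and that the primary result is therefore biased. The documents do not support either statement. The plan does not prescribe a complete-case analysis; it is silent. Section 8.5 asks for an IOP at withdrawal, so many who leave may have a reading that could be used. The all-operated wording can also be read as defining a population, with missing values left for later.

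Nor do the documents predict unequal loss. The 10% is an upper bound without a split. Section 9.4 keeps subjects with a repositioned or replaced device in follow-up, and Section 9.2 lets medication be restarted on study, so poor control need not mean leaving. The 20% vs 0% case places all loss in one arm. At 15% vs 5% the bias is small beside the standard error.

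The recovery to 1.5 in step 3 also follows from the set-up, since loss there depends only on an observed Month-9 value; step 4 shows the limit. It would likewise be wrong to claim that a mixed model restores the power of 40 per arm: the SD of the estimate falls only from about 0.70 to 0.68–0.69.

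All of this stands and limits the size of the point. It does not remove the gap. Silence leaves the choice open, the withdrawal visit is requested rather than assured, and a subject lost without it has no late value at all.

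**Conclusion.** The gap is certain: Sections 11.1 and 11.6 promise a set that the Section 11.2 method does not deliver, and no section says how missing Month-12 or early-withdrawal IOP is handled. The bias is conditional. It requires loss related to IOP and differing between arms in rate or reason. The unmasked design, and the investigator's power under Section 8.5 to withdraw subjects, make that plausible, not expected.

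Under the assumed patterns in which the higher-IOP arm loses more, the understatement of a 1.5 mmHg difference runs from essentially nothing at equal loss to 0.28–0.40 mmHg (19% to 27%) at the most unequal split; with the arms reversed it becomes an overstatement. The change should be made because it is cheap and removes a choice that would otherwise be made with arm-labelled data in hand. The argument does not rest on gained power.

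**What to change.** In Section 11.2:

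1. Replace the t-test with a mixed model for repeated measures on IOP at Months 1, 3, 6, 9 and 12, with terms for arm, visit, arm × visit and baseline IOP × visit. Name the between-arm Month-12 contrast as the primary estimate. This also removes the paired test, which does not suit two independent arms.
2. Assign early-withdrawal IOP to the visit window in which it was taken, never to Month 12 by default. The Section 8.3 windows leave gaps (Month 3 ends at day 90 + 14 = 104; Month 6 opens at 180 − 14 = 166), so state a rule for readings that fall between them.
3. Add a sensitivity analysis for informative dropout that lets unseen Month-12 values be worse than predicted, by differing amounts in the two arms.
4. Align the analysis-set wording in Sections 11.1 and 11.6 with what the model includes.

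The cost is SAP wording and somewhat more analysis work. The model relies on data being missing at random, a weaker assumption than complete-case analysis makes, but still an assumption. Operated subjects with no IOP at any modelled visit will still not contribute, and the plan should say so.
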